7.4. Mock Scanner Training

As part of the study, participants will engage in a mock scanner training session. The purpose of this session is to acclimate participants to the scanner and to assess their comfort level, minimize any anxiety, and provide practice and training on all tasks that will be conducted in the real MRI environment. Training in the mock scanner will take approximately 20 minutes and will occur prior to a subject's first imaging session. After the session, any questions or concerns will be discussed. Participants may be excused from the mock scanner training at subsequent study visits.

7.5. Incidental Findings by MRI

The study subjects to be recruited for this study are cognitively healthy. Sometimes, however, a few incidental abnormalities may be found in these study subjects, such as brain tumors, vascular lesions, moderate to severe white matter lesion load, and other neuroradiological abnormalities that would preclude subjects from being included in the analysis, or that are clinical abnormalities requiring follow-up. These subjects will be advised to see their physicians for formal assessment. [name] is a board-certified neurologist at MCW. He or a Co-I (MD) will consult with the subjects in such cases.

7.6. Subject Safety

Due to the duration and the low doses of AGB101 administered in this study, we anticipate this study to be at minimal risk to the volunteer. We do not expect frequent or severe AEs to be present. Subjects will be instructed to call the study site for intercurrent illnesses. All AEs will be monitored according to the Safety Plan (see Section 7.1). The DSMB board will review the initiation frequency and severity of any AEs. Stopping rules will be invoked for the subject and study if AE are reported above the 5% threshold. Subject safety will be ensured during the study period, and the study may be closed with regular visits to the resolution of the AE. Safeguards to ensure subject confidentiality will consist of maintaining records in a locked cabinet in a locked room in the Department of Neurology research offices. All computers are password protected to further ensure safety.

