7. DATA SAFETY MONITORING PLAN

An appointed DSMB will discuss the ethical conduct of the trial, review event definitions and the subject ICF form, and further develop plans for monitoring the data and safety of the trial. The DSMB will meet at least every six months to review the course of the trial and interim data. The DSMB agrees to communicate with institutional review board (IRB)/human subject committees to provide reassurances, as appropriate. There will be three DSMB members with the following areas of expertise:

- Neural mechanism underlining learning and memory in aging and neurological disease
- Aging and memory loss
- Psychology and neuroimaging

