7.1.2 Definitions and Criteria

7.1.3 Adverse Events

Per International Conference on Harmonisation (ICH) E2A: An AE is any untoward medical occurrence in a subject or clinical investigation subject administered a pharmaceutical product and which does not necessarily have to have a causal relationship with this treatment. An AE can therefore be any unfavorable and unintended sign (including an abnormal laboratory finding, for example), symptom, or disease temporally associated with the use of a medicinal product, whether or not considered related to the medicinal product.

Events meeting the definition of an AE **include**:

- Exacerbation of a chronic or intermittent pre-existing condition including either an increase in frequency and/or intensity of the condition
- New conditions detected or diagnosed after investigational product administration even though it may have been present prior to the start of the study
- Signs, symptoms, or the clinical sequelae of a suspected drug interaction
- Signs, symptoms, or the clinical sequelae of a suspected overdose of either investigational product or a concomitant medication

Clinically significant abnormal findings (laboratory test results, vital signs, physical examination findings, ECGs, radiologic exams, or other studies) should be recorded as AEs. A "clinically significant" finding is one that affects clinical management, including additional visits, monitoring or referrals, diagnostic tests or alteration of treatment, or that is considered clinically significant by the investigator. A clinically significant finding may be a change in a test that has previously been abnormal but now requires additional action.

When a medical or surgical procedure is performed, the condition that leads to the procedure should be recorded as the AE.

Events that **do not** meet the definition of an AE include:

- Anticipated day-to-day fluctuations or expected progression of pre-existing disease(s) or condition(s) present or detected at the start of the study unless judged by an investigator to be more severe than expected for the subject's underlying condition
- Abnormal laboratory, ECG, or vital sign measurements that are not labelled clinically significant (see definition above)
- Situations where an untoward medical occurrence did not occur (social and/or convenience admission to a hospital)
- Pregnancy
- Overdose in the absence of other AEs will not be reported as an AE in its own right

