7.1.6 Reporting Procedures and Requirements

Adverse Events

AE recording will begin after the first dose of study drug is administered the morning after baseline. Thereafter, AEs will be ascertained by asking the subject how he/she has been since the last visit. Any AEs occurring before the start of treatment (ie, before the first dose of the study drug) will be recorded in the medical history only. If the investigator detects an AE in a study subject within 1 month (4 weeks, -/+ 1 week) of the last scheduled follow-up visit this will also be collected. All AEs will be followed until resolved or stable and the outcome documented on the CRF.

Also, the sign, symptom, or disease present before starting the treatment period are only considered AEs if they worsen after starting the treatment period.

The investigator should report all information about AEs on the AE/SAE section of the Case Report Form (CRF). Whenever possible, an AE will be reported using a diagnostic term (eg, “common cold” or “upper respiratory infection” rather than “runny nose, cough, mild fever”) and should be described with the attributes.

Serious Adverse Events

Each AE will be assessed to determine whether it meets seriousness criteria (Section 7.1.2.2). If the AE is considered serious, the investigator should report this event to Agene Biotech as outlined below and to the Institutional Review Board (IRB) & Data Safety Monitoring Board (DSMB) according to their standard operating procedures.

All information about SAEs will be collected and reported by entering the SAE information in the AE CRF. The investigator should send the initial report to the Site PI and to Agene Biotech within 24 hours of becoming aware of the SAE and followed by follow-up reports as soon as possible, whether the events are deemed related to the study drug or not. The information provided in the AE system should be as complete as possible, but minimally it must contain the following:

- Subject number
- Brief description of the SAE (diagnosis or signs/symptoms)
- Serious criteria
- Causality assessment
- Assessment of the intensity of the event

Agene Biotech will receive notification of the initial SAE via an e-mail from MCW Study Team. Site personnel will complete the paper SAE report form, scan and e-mail it within 24 hours to the following address: [contact]

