SAEs that are ongoing should be followed until resolved or stabilized to a level acceptable to the investigator. Information not available at the time of the initial report (eg, an end date for the AE, laboratory values received after the report, or hospital discharge summary) must be documented on a follow-up form. All follow-up information must be reported in the same timelines as initial information.

Any SAEs considered related to the study drug and discovered by the study team at any interval after the study must also be reported to the Agene Biotech within 24 hours following knowledge of the event.

Sponsor Reporting of Suspected Unexpected Adverse Reactions to Regulatory Authorities (SUSAR)

Per 21 CFR 312.32[c](1)(i)) the Sponsor (MCW) must report in an **IND Safety Report** any suspected adverse reaction to study treatment that is both serious and unexpected. Before submitting an IND safety report, the Sponsor needs to ensure that the event meets all three of the definitions:

- Suspected adverse reaction
- Serious
- Unexpected

The Sponsor/MCW Study Team will submit a **FDA Form 3500A MedWatch** for expedited reporting of all events that qualify for expedited reporting. Refer to the Form FDA 3500A Supplemental Manual for instructions and timelines on mandatory reporting.

Unblinding Treatment Allocation

Generally, only SUSARs for which the treatment allocation of the subject is unblinded should be reported by the sponsor to the pertinent regulatory authorities.

When an event may be a SUSAR, the blind should be broken only for that specific subject, and only if knowledge of the study drug assignment is material to the medical management of the AE. When unblinded to assist in the medical management, the blind for that subject should be maintained for individuals responsible for the ongoing conduct of the study (eg, management, monitors, and investigators) and those responsible for data analysis and interpretation of results at the conclusion of the study (eg, biometrics personnel).

Unblinded information should only be accessible to those who need to be involved in the safety reporting to pertinent regulatory authorities, independent ethics committees/independent review boards (IRBs) and DSMBs, or individuals performing ongoing safety evaluations during the study.

Reporting to Institutional Review Board and Data Safety Monitoring Board

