The IRB/DSMB will be notified of any SUSARs according to local regulations and within the designated timeframe. Refer to MCW IRB Reporting Policy. These will be reported to the DSMB in parallel.

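### The only numerical stopping rule (Protocol 7.6, a 5% AE limit) leaves AE class, unit, denominator and window undefined, so it cannot be applied consistently and on its literal reading may fire on background events

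*Protocol*

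**What the plan says.** Protocol section 7.6 (Subject Safety) says: "Stopping rules will be invoked for the subject and study if AE are reported above the 5% threshold". Nothing else in the section defines the trigger. The sentence before it has the DSMB review how often AEs occur and how severe they are. The one after it allows the study to be closed, in permissive wording.

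Other sections bear on how the sentence would be read:

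- **What counts as an AE.** Section 7.1.3 includes an untoward event "whether or not considered related to the medicinal product".
- **When AEs are recorded.** Section 7.1.6 says "AE recording will begin after the first dose of study drug is administered the morning after baseline". Table 1 continues AE collection through both treatment periods and the washout, and adds a telephone call about 4 weeks after the last dose.
- **AE classes.** Sections 7.1.4 and 7.1.5 define seriousness, intensity and relationship, and 7.1.1 puts them on the AE form. None is tied to the 5%.
- **Other safety routes.** Section 7.1.6 sends SAEs to the IRB and the "Data Safety Monitoring Board (DSMB) according to their standard operating procedures". The sponsor must report to FDA "any suspected adverse reaction to study treatment that is both serious and unexpected". For notifications of such reactions to the IRB, it adds: "These will be reported to the DSMB in parallel". Section 7 lets the DSMB "further develop plans for monitoring the data and safety of the trial".

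The SAP text available for review ends at the opening of section 7 and contains no stopping criterion.

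**The concern.** The sentence commits the trial to act at a number without saying what is being counted. It could mean the share of subjects with any AE, the share of subject-periods, or the share with one particular AE term. It could apply to all 50 subjects or to those enrolled so far. It could cover AGB101 exposure only, or all recorded time. It also applies the limit to an individual subject, for whom a percentage has no meaning.

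The literal any-AE reading takes in minor events unrelated to drug. Section 7.1.6 uses the common cold as an example of an AE term. Nominal recorded time is 2 + 4 + 2 + 4 = 12 weeks, of which 2 are on AGB101. A few colds during placebo, washout or follow-up would therefore meet the rule.

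An undefined rule leaves the sponsor and DSMB two poor choices: stop on background noise, or settle the meaning of 5% after the events are known.

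**Working it through.** **Inputs from the documents.** Limit strictly over 5% (7.6); 50 subjects (Protocol Summary); AEs counted regardless of cause (7.1.3); levetiracetam AE rates by term at 1000–2000 mg daily of 9, 4, 5, 5, 6 and 7% (7.1); study dose 220 mg. The 5% is stated without derivation, so there is no planned figure to reproduce.

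**Assumed.** The documents give no any-AE rate at 220 mg. Rates of 2, 5 and 10% per subject are used, with and without an added 5 points for drug.

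**Step 1: trigger count.** Take the smallest r with r/n > 0.05.

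| Subjects counted | Trigger | Check |
|---|---|---|
| up to 19 | 1 | 1/19 = 5.3%; 1/20 = 5.0% is not over |
| 20 to 39 | 2 | 2/39 = 5.1%; 2/40 = 5.0% is not over |
| 40 to 50 | 3 | 2/50 = 4.0%; 3/50 = 6.0% |

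**Step 2: any-AE reading, 50 subjects.** P(X ≥ 3) = 1 − Σ C(50,k) p^k (1−p)^(50−k), k = 0 to 2. At p = 0.05: 1 − (0.0769 + 0.2025 + 0.2611) = 0.459.

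| Background rate | No drug effect | Plus 5 points |
|---|---|---|
| 2% | 0.078 | 0.689 (p = 0.07) |
| 5% | 0.459 | 0.888 (p = 0.10) |
| 10% | 0.888 | 0.986 (p = 0.15) |

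At 2% the rule discriminates usefully. At 10% it fires almost regardless of drug.

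**Step 3: per-term reading.** Scale each rate in 7.1 by 220/1000 or 220/2000, with zero background. Pharyngitis becomes 1.98% or 0.99%. At the 1000 mg scaling, P(3 or more of 50) by term, in the order above, is 0.077, 0.010, 0.018, 0.018, 0.028 and 0.042. With terms independent, P(any term triggers) = 1 − Π(1 − P_j) = 0.179. At the 2000 mg scaling it is 0.031. Because background is zero here and not in Step 2, the two steps show that the reading matters; they do not measure by how much.

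**Step 4: example replacement counts.** Classify each subject by worst related AE: serious with probability s (a fraction f of these fatal or life-threatening) or severe but not serious with probability v. The study pauses at 1 fatal or life-threatening, 2 serious, or 3 serious or severe. Then

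P(pause) = 1 − Σ n!/(i! j! (n−i−j)!) [s(1−f)]^i v^j (1−s−v)^(n−i−j), over i = 0, 1 and j = 0 to 2−i.

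At s = v = 0.01, f = 0.2, n = 50: 1 − (0.364 + 0.186 + 0.046 + 0.149 + 0.074) = 0.181.

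| s = v | 50 exposures | 100 exposures |
|---|---|---|
| 0.5% | 7% | 18% |
| 1% | 18% | 45% |
| 2% | 45% | 83% |
| 3% | 68% | 96% |
| 5% | 92% | over 99% |

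The 100-exposure column is an upper guide for counting both periods. It takes the placebo-period rate as equal to the AGB101 rate and treats periods as independent. The one-fifth share is assumed: at 1% plus 1% with 50 exposures, f = 0 gives 12.5% and f = 0.5 gives 26%.

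**The case against.** The strongest case is that the over-triggering result depends on one reading. Section 7.1 quotes AE rates only by term, from 4% to 9%, so a per-term 5% is at least as natural, and on that reading the rule fires seldom. The background rates are also assumed, and 7.6 itself expects AEs to be infrequent; at 2% the rule performs reasonably. An over-sensitive limit errs toward review. The DSMB also reviews AEs, may write a fuller plan not seen here, and section 7.10 has the IRB and principal investigator told of unexpected AEs at any time.

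Most of this stands as a limit on size. It does not remove the defect: two natural readings lead to different actions, and none of the other routes says when to stop.

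Three stronger inferences are tempting but not supported:

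- **That the rule would probably halt this trial.** That needs the any-AE reading and a common background, and the documents give neither.
- **That the two-monthly AE analyses in 7.8 multiply the chance of crossing.** Section 7.8 does not say the 5% is applied at those analyses.
- **That serious harm would slip under 5%.** Two serious reactions among 50 stay under the limit only if the other 48 subjects have no AE: 0.98^48 = 38%, 0.95^48 = 9% and 0.90^48 = 0.6% at 2, 5 and 10% background. SAE reporting and DSMB review would still apply.

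**Conclusion.** The concern holds as a defect of definition with potentially large consequences. Section 7.6 cannot be applied as written: it fixes no AE class, relatedness, unit, denominator or window, and its subject-level limb has no meaning. On the literal any-AE reading, whether it separates drug harm from background turns on a rate the documents do not supply, and it does so poorly once that rate is near 10%. The per-term result rests on zero background, linear dose scaling and independent terms. The documents do not select either reading, so neither set of probabilities should be quoted as the rule's actual performance. Other safety reporting is in place, so this should be corrected but does not show that subjects are unprotected.

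**What to change.** Replace the sentence in 7.6 with two rules.

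- **Subject:** stop study drug for any serious or severe AE that the investigator judges related.
- **Study:** pause for DSMB review at any related fatal or life-threatening AE, or at a pre-specified small count of subjects, for example the second with a serious related AE or the third with a serious or severe related AE.

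State that related means the investigator's judgement, because 7.1.5 otherwise accepts timing alone for analysis.

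Count events in either treatment period, from first dose to 7 days after the last, without regard to assignment. A 14-day period plus 7 days reaches day 21, which covers the skin reactions that 7.1 places at days 14–17. Counting AGB101 events only would let a pause, or its absence, reveal a subject's treatment, against 7.1.6: "Unblinded information should only be accessible to those who need to be involved in the safety reporting". The Investigational Drug Service, which already controls the blind (4.1), gives the AGB101 and placebo split to the DSMB only, and the DSMB decides on stopping.

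The counts above are a starting point. The sponsor and DSMB should set them and print the pause probability across a range of rates beside the rule, as in the last table of the working.

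The cost is protocol wording, a DSMB agreement and one AE table by treatment. Seriousness, severity, relationship and dates are already collected (7.1.1). The rule becomes less sensitive to clusters of mild AEs, which the DSMB still reviews, and some pauses will be for placebo-period events.

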7.8. Data

AE data analysis will be performed every 2 months. Plans for unexpected problems involving risk to participants or others will consist in notification of the principal investigator in order to activate appropriate medical or professional intervention as needed.

7.9. Efficacy

Evaluation of efficacy will consist of measurement of brain connectivity at the interim point when recruitment has reached 50% of subject with a second fMRI session. Secondary outcome measure of cognitive

assessment will also be reviewed. It is anticipated, however, that with the short, 2-week treatment period, statistical significance may not be reached.

7.10. Feedback Mechanism

Evaluation and response to subjects' complaints will be routinely addressed by the DSMB. The IRB and principal investigator will be notified of significant protocols violations and emergence of unexpected AEs at any time during the study. In addition, a report by the DSMB will be provided to the IRB at the end of the study.

Table 1. Schedule of study procedures.

	Screening^h	Baseline	Period 1^b	Washout^c	Period 2^{b,d}
Visit	-1	1	2 ^e	3 ⁱ	4 ^e
Duration			2 weeks	4 weeks	2 weeks
Informed Consent #1 ^a	X				
Blood (or Buccal Swab) for APOE	X				
Demographics	X				
Medical History	X				
Informed Consent #2 ^a		X			
Inclusion/Exclusion Criteria		X			
NeuroExam	X				
Vital Signs	X	X	X	X	X
C-SSRS	X		X		X
MOCA, RBANS	X				
Neuropsychological Battery		X	X		X
Neuroimaging Assessments (fMRI) ^f		X ^g	X		X
Blood Draw for AGB101 level			X	X	X
Randomization		X			
Dispense Medication		X		X	
Administer Study Medication			X		X
Medication Compliance			X		X
Adverse Events	X	X	X	X	X ^f

^a The ICF administered at the screening visit will address the blood (or buccal swab) for APOE and other screening procedures. If the study subject is eligible to enroll in the study, a separate ICF administered at the baseline visit will address the remainder of the study.

^b Study procedures will take place on the last day of each 2-week treatment period.

^c Medication is dispensed and other procedures obtained on the last day of the 4-week (-/+ 1 week) washout period.

^d In the case of early termination, the Period 2 procedures will be performed.

^e Visit takes place on the last day of the study period which may be a minimum of 14 days and a maximum of 21 days.

^f Prior to each fMRI scan, subjects will undergo MRI safety screening.

^g Subjects will undergo mock scanner training. At subsequent visits, the subject may be excused from mock scanner training.

^h Screening activities may be split into 2 or more visits as needed (i.e. separate visit for APOE testing only and subsequent screening visit(s) for other screening procedures). Informed Consent #1 will be obtained prior to all activities at the first screening visit. With the exception of APOE genetic testing, all other screening procedures must be repeated if greater than 3 months elapse from the date of the first screening procedure.

ⁱ Start of Period 2 will be a minimum of 21 days and a maximum of 35 days post the date of the last dose of Period 1. (i.e. Washout period of 4 weeks, -/+ 1 week window permitted for scheduling purposes)

^f Telephone call to subject at 4 weeks post last dose in Period 2 (-/+ 1 week) to assess for AEs and AE outcomes.

5.4.6. Blood Draws

All subjects will undergo a blood draw at the last day of each treatment period and on the last day of the washout period. Samples will be labeled with the study name, study visit number, contents of each collection vial, and the date of collection. Tubes may also be labeled with a barcode for sample management.

5.4.7. Randomization, Study Drug Dispensation, Administration, and Compliance

The Investigational Drug Service at Froedtert Hospital will randomize participants to the treatment conditions.

In Period 1, all study participants will receive treatment with either AGB101 (220 mg, orally, QD) or placebo; in Period 2, all subjects will crossover and receive the other treatment. This is a double-blind study, so both the participants and study team will be blind to the treatment received.

All study treatments (drug and placebo) are dispensed in identical nondescript tablets by the Investigational Drug Service at Froedtert Hospital. Tablets are provided for daily morning doses. Study drugs will be dispensed at baseline and on the last day of the 4-week (-+ 1 week) washout period. Subjects will be asked to self-administer treatment QD, once in the morning.

Treatment compliance will be monitored by participant self-report at the end of each treatment phase, bottle return and pill count, and analysis of AGB101 blood values at each visit during the study protocol.

Data Management

6.1. The Froedtert Hospital Investigational Pharmacy system will be used to enroll patients and obtain the randomly assigned treatment group. Data forms will be printed, completed, and entered into a database. The database will be monitored for completeness, consistency, accuracy, and timeliness. No patient-identifying information will be stored in the database. To ensure that data are secure from external violation, computer systems containing study data will be password protected, and physical access to the computer systems will be limited.

6.2. Determination of Changes in Network Activity and Concurrent Improvement in EM. The cognitive and MRI/rfMRI datasets will be obtained at baseline (before placebo/AGB101 administration) and on the last day of each 2-week treatment period. These two time points will be denoted $t = 1, 2$. The two 25-subject groups, both of which will receive both placebo and AGB101 at different treatment phase, will be denoted $g = 1, 2$. The set of EM scores for subject s , from group g , at time t will be denoted $Cog(s,g,t)$, where $s = 1, \dots, 25$; $g = 1, 2$; and $t = 1, 2$. The HFC calculated between the hippocampus and the bilateral sensorimotor cortex for subject s , from group g , at time t will be denoted $HFC(s,g,t)$.

6.3. Functional-Connectivity Changes Due to Perturbation. We employed age, years of education, gender, and gray matter (GM) volume as time-invariant covariates to obtain residual variables to determine the HFC changes due to perturbation. We will model the HFC as a function of these nuisance regressors, using the following multiple linear regression equation, and retain the residuals as $HFC_{Res}^+(s, g, t)$ for further analysis:

$$HFC(s, g, t) = \beta_0 + \beta_1 Age(s) + \beta_2 Edu(s) + \beta_3 GM(s) + \beta_4 CSF(s) + \beta_5 Gender(s) + Res(s, g, t),$$

where $\widetilde{HFC}^+(s, g, t) \equiv Res(s, g, t)$. This regression will be performed using all of the data (i.e., all subjects, all groups, and all times). The GM measurement will be conducted with GM concentration and hippocampal volume measurement, as described in our publication and others (71-74). We will test the residuals $HFC^+(s, g, t)$ using three-factor crossed-nested analysis of variance (ANOVA), with fixed factors of group and

time and a random factor of *subject* nested within *group* (i.e., all subjects will be tested at all times, but the placebo and AGB101groups will contain different treatment phases). We will test for both group and time main effects, as well as for the group \times time interaction. If we find significant main effects or interactions, we will perform post hoc procedures to determine which time and group (i.e., placebo vs. AGB101) combinations are significantly different. In addition to the HFC analysis, we will conduct a DMN analysis 75).

6.4. EM Changes Due to AGB101Perturbation. The two EM scores (AVLT and LMT) will be normalized to Z-score by transforming individual raw test scores according to the mean and standard deviation of the scores for all subjects. Then, Z-scores of each test will be averaged to obtain individual composite memory Z-score, as we have previously published (76). Similar to the above model for HFC changes due to AGB101perturbation, we will model the Cog score, using the time-invariant covariates as nuisance regressors:

$$\Delta EM(s, g, t) = \beta_0 + \beta_1 Age(s) + \beta_2 Edu(s) + \beta_3 GM(s) + \beta_4 CSF(s) + \beta_5 Gender(s) + Res(s, g, t)$$

Define $\widehat{\Delta EM}(s, g, t) \equiv Res(s, g, t)$. We will test the residuals $\widehat{\Delta EM}(s, g, t)$ using a *three-factor crossed-nested* ANOVA, with fixed factors *group* and *time*, and random factor *subject* nested within *group*. We will test for group and time main effects, as well as the group \times time interaction. If we find significant main effects or interactions, we will perform post hoc procedures to determine which time and group combinations are significantly different.

6.5. Prediction of Changes in Correlation Between HFC and EM Before and After AGB101Perturbation. A multiple linear regression is used to model EM as a linear function of HFC and test the difference in slope and intercept between the AGB101and placebo groups. If the subject is in the AGB101group, $I(s, g) = 1$; if the subject is in the placebo group, $I(s, g) = 0$.

$$EM(s, g) = \beta_{0,0} + \beta_{0,1} I(s, g) + \beta_{1,0} HFC(s) + \beta_{1,1} HFC(s)I(s, g) + Res(s)$$

Here, **HFC(s)** represents baseline HFC for subject s (for simplicity, nuisance regressors are not shown).

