4.1. Overall Design

This study will test the hypothesis that **decreased abnormal hyperfunctional connectivity can be correlated with improved EM using a daily, low-dose LEV perturbation (AGB101 levetiracetam extended release)**. In this study, there are two study groups: APOE 4 carriers ($n=25$) and APOE4 noncarriers ($n=25$). The functional connectivity changes in HFC will be determined in a randomized, double-blind, placebo-controlled crossover manner, in which a low dose of AGB101 levetiracetam extended release (220 mg, QD) or placebo is administered to 50 healthy 55-75-year-old subjects (comprising 25 APOE 4 carriers and 25 noncarriers), with the order of treatments counterbalanced in a within-subject crossover design, as illustrated in

Fig. 2 below. The study procedures are almost identical to those described in Refs (77, 78). In brief, study participants will receive placebo during one treatment period and AGB101 levetiracetam extended release during the other treatment period, with the order of treatments counterbalanced (randomized, double-blind).

Figure 2. Study design and AGB101 treatment protocol

Notes: Of the 50 subjects, 25 are APOE 4 carriers and 25 are noncarriers.

See Table 1 for timing and schedule of procedures.

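### Removing covariates in a first step that omits group shrinks the carrier–noncarrier main effect (about 10% by chance, 18% if the pilot age gap recurs); HFC change contrasts are untouched

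*SAP*

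**What the plan says.** Section 6.3 has the same text in the Protocol and the SAP. It uses age, education, gender and GM volume "as time-invariant covariates to obtain residual variables to determine the HFC changes due to perturbation". The equation also contains CSF, which that list omits, and it has no group term. On the fit it states: "This regression will be performed using all of the data (i.e., all subjects, all groups, and all times".

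The residuals then go into an ANOVA with fixed factors group and time and with subject nested in group. "We will test for both group and time main effects", the plan says, along with the interaction, and "If we find significant main effects or interactions, we will perform post hoc procedures".

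Section 6.4 repeats the two steps for memory. The left-hand side of its equation is ΔEM, although the text speaks of modelling the Cog score. Again: "We will test for group and time main effects, as well as the group" × time interaction.

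The documents describe group in two ways:

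- **Genotype.** Protocol 4.1 says "there are two study groups: APOE 4 carriers" and noncarriers, 25 each. SAP 6.2 refers to "The two 25-subject groups, both of which will receive both placebo and AGB101 at different treatment phase", which fits genotype and does not fit treatment.
- **Treatment.** The post hoc sentence in 6.3 asks which "time and group (i.e., placebo vs. AGB101) combinations are significantly different".

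**The concern.** When covariates are regressed out before group enters, they absorb whatever part of the group difference overlaps them. The second step does not give that part back. Only a model that fits group and covariates together divides the overlap properly.

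Genotype is not randomised, so overlap is to be expected. In Protocol 3.3 the pilot carriers were younger than the ε3ε3 comparators, and Protocol 1.1 names reduced brain volume as an APOE 4 pattern.

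Three things are at stake:

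- The group main effect is tested for both HFC and EM, and a significant result is one of the triggers for post hoc comparisons.
- Post hoc comparisons of carriers with noncarriers at a single time point are distorted too. This matters because the primary objective is framed as normalization in carriers.
- If ΔEM is a change score, its group effect is shrunk as well.

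**Working it through.** The documents give no figure for this point, so there is none to reproduce. Group is read as genotype and data are taken as complete.

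**Identity.** Let g be the genotype indicator, X the covariates with intercept, y the subject means, and M the matrix that takes residuals on X.

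- Joint estimate: b_joint = g′My / g′Mg.
- Two-step estimate (difference in mean residuals): b_two = g′My / Σ(g − ḡ)².
- Since g′Mg / Σ(g − ḡ)² = 1 − R², b_two = (1 − R²) × b_joint.

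The two-step estimate is therefore never larger in size than the joint one. It can still exceed the unadjusted difference. In one simulated data set the unadjusted effect was 0.189, the two-step 0.4425 and the joint 0.5632, a ratio of 0.786 = 1 − 0.214. The identity held to rounding error in simulation.

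**HFC change contrasts.** The covariates carry only the subject index, so the fitted value is the same at both times and cancels: Res(s,2) − Res(s,1) = HFC(s,2) − HFC(s,1). Time and group × time effects are neither biased nor sharpened.

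**Chance imbalance.** With n = 50 and p covariates unrelated to genotype, R² follows Beta(p/2, (n − 1 − p)/2), with mean p/(n − 1).

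- Five covariates (the equation): 5/49 = 10.2%; 10th to 90th percentile 3% to 18%.
- Four covariates (the text list, without CSF): 4/49 = 8.2%.

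**Pilot age gap** (Protocol 3.3: 66.62 ± 5.84, n = 21; 70.11 ± 5.23, n = 27).

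- Gap = 70.11 − 66.62 = 3.49 years.
- Pooled SD = √[(20 × 5.84² + 26 × 5.23²)/46] = 5.50; d = 3.49/5.50 = 0.63.
- t = 3.49 / [5.50 × √(1/21 + 1/27)] = 2.18 on 46 df, p = 0.034.
- If this gap holds in the population sampled, age R² = (3.49²/4) / [3.49²/4 + (5.84² + 5.23²)/2] = 0.090. Adding chance overlap: 0.090 + 0.910 × 5/49 = 0.183.
- If the trial sample shows exactly this gap, age R² = 0.094, and the total with four other covariates is 0.094 + 0.906 × 4/48 = 0.169.

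**Effect on the test** (20,000 simulations per scenario, residual SD 1 on subject means, nominal 5%; effect sizes are assumptions):

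| Scenario | Mean R² | Two-step estimate of 0.80 | Null rejection, two-step | Power at 0.8 SD, two-step v joint | Power at 0.5 SD, two-step v joint |
|---|---|---|---|---|---|
| Chance only | 10% | 0.72 | 5.2% | 74 v 75 | 38 v 38 |
| Half the pilot age gap | 12% | 0.70 | 4.9% | 72 v 73 | 35 v 36 |
| Full pilot age gap | 18% | 0.65 | 4.0% | 66 v 70 | 31 v 35 |
| Full gap plus assumed 0.4 SD GM gap | 21% | 0.63 | 3.7% | 62 v 69 | 28 v 33 |

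The joint model averaged 0.80 in every scenario and rejected 5.0 to 5.2% under the null. Before rounding, the power loss at 0.8 SD runs from 0 to 6 points.

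**Single time points.** The two-step method moves the carrier–noncarrier gap by the same absolute amount at each time, R² times the joint effect averaged over times. Take illustrative gaps of 0.8 before and 0.2 after treatment, and R² = 0.18. The shift is 0.18 × 0.5 = 0.09, so the gaps become 0.71 and 0.11. The change is still 0.6, but the remaining gap looks about half its size.

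**The case against.** The algebra is not in dispute; the case against is about importance.

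- **The test hardly moves.** With chance imbalance alone, power and null rejection are nearly the same as in the joint model. With larger imbalance the test is conservative, so no extra false claims follow. This stands. The defect is mainly in the estimate.
- **The primary contrast is untouched.** This stands too. The group main effect also averages over on-treatment scans, so it is not a clean measure of baseline hyperconnectivity.
- **Group may mean treatment.** Then each completer contributes to both levels, the covariates balance exactly and nothing shrinks. But Protocol 4.1, SAP 6.2 and the nesting of subject within group all point to genotype. The conflicting label in 6.3 has to be reconciled either way.
- **The 18% is soft.** It carries over a small pilot with ε3ε3 comparators. If pilot ages are treated as normal and cut to the trial's 55–75 range, the gap falls to about 2.5 years and total R² to about 16.5%. It is an illustration, and the 0.4 SD GM gap is purely assumed. The 10% needs no pilot figure.
- **The joint estimate is not automatically the right one.** If lower GM is part of what APOE 4 does, adjusting for it changes the question. This stands and is the reason to report the effect with and without GM.

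**Conclusion.** The concern holds as a secondary point. If group is genotype, the plan as written understates the jointly adjusted genotype main effect on HFC. The mean shrinkage is 10% with five covariates unrelated to genotype, 8% without CSF, and about 18% if the pilot age gap recurs. These are averages over possible samples; in any one sample the factor is exactly 1 − R². The cost in power is 0 to 6 points at an assumed 0.8 SD, with a conservative test under larger imbalance.

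The HFC time and group × time contrasts are unaffected with complete data, so the stated purpose of the covariate step, to inform HFC change, is not served. For EM, the group effect is shrunk by the same factor if ΔEM is a change score.

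**What to change.** - Delete the separate residual step in 6.3 and 6.4. Fit one mixed model with genotype, time or treatment, their interaction, the covariates and a random subject effect.
- Define group once and remove the conflicting label. State whether ΔEM is a change score.
- State whether CSF is a covariate. Report the genotype effect with and without GM.
- If the covariates are meant to inform the change contrasts, prespecify covariate-by-time or covariate-by-treatment terms. Main-effect covariates cannot do this.

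This removes the shrinkage from the genotype main effect and leaves the HFC change contrasts as they are. The cost is wording in the Protocol and SAP and a change of analysis code, with no new data.
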